7.2 Handling of missing data, drop-outs, extreme values and protocol violations

For an overview of checks for identification of protocol violations and data review, please refer to the data review plan.

8 Data analysis

8.1 Statistical software

Statistical analysis will be performed using R statistical software, version 4.3.2 or higher (https://www.r-project.org/) on a Windows 7 (or higher) personal computer. The calculation of pharmacokinetic parameters will be performed with WinNonlin, version 8.4, Pharsight Corporation, Mountain View, CA.

For each script/test performed using R, the Rmarkdown function will be used to document the output of the computerized system for future reference.

8.2 Definitions, derived variables and handling of missing data

Definitions of time points / time windows

Baseline will be defined per parameter and will be the value/measurement at the following timepoints:

Parameter for	Timepoint
Demographics	Screening
Vital signs	Baseline (before IMP administration)
ECG	Baseline (Screening)
Local laboratory assessment	Baseline (before IMP administration)
Arterial blood gas analysis	Baseline (before IMP administration)

Filing: https://fourteenfour.dhcvisioncloud.com/dhcvision/document.jsp?key=DATABASE:1001;IO:1527897	Page 11 of 22
---	---------------

Form Valid From: 08/03/2024

Form Version:

Record Title:

Record Title: Clinical Statistical Analysis Plan CT-P1-001

Parameter for	Timepoint
Biomarker (DPP3 concentration and	Baseline (before IMP administration)
activity)	

Derived variables

Extent of exposure:

Extent of exposure will be defined as total exposure in mg and calculated as:

total exposure
$$[mg] = 20 \frac{mg}{ml} * IMP volume [ml] * factor$$

where IMP volume is the body weight adjusted IMP volume before addition of NaCl and factor equals 1 for treatment group 12 mg/kg AK1967, 1/2 for treatment group 6 mg/kg AK1967, and 1/4 for treatment group 3 mg/kg AK1967. Total exposure will not be calculated for the Placebo treatment group.

In case of premature termination of the infusion, total exposure will additionally be multiplied by $\frac{volume\ administered\ [ml]}{c}$ in order to account for only partly administration of study drug.

Exposure per kg body weight will be calculated as:

Exposure per kg body weight
$$\left[\frac{mg}{kg}\right] = \frac{total\ exposure\ [mg]}{body\ weight\ [kg]}$$

Body mass index (BMI):

$$BMI = \frac{Weight [kg]}{Height [m]^2}$$

Handling of missing values

Data from subjects who prematurely terminate the trial will be used to the maximum possible extent. Missing values will not be inputted.

8.3 Disposition

An overview of all subjects who entered the study, who were randomized and who completed the study will be provided by treatment group and overall.

Demographic data, screening and baseline characteristics

Demographic data and baseline characteristics will be summarized for the safety analysis set. Screening data (prior to study participation) will be shown as listings.

Filing: https://fourteenfour.dhcvisioncloud.com/dhcvision/document.jsp?key=	DATABASE:1001;IO:1527897	Page 12 of 22
---	--------------------------	---------------

Form Valid From: 08/03/2024

Form Version: 1

TOTTI VCISIOTI.

Record Title: Clinical Statistical Analysis Plan CT-P1-001

Record Title:

Demographic data and baseline characteristics

Summary statistics will be presented for age, weight, height, BMI, vital signs at screening and baseline (body temperature, heart rate, MAP, systolic and diastolic blood pressure, respiratory rate), Hb, Hct, leukocytes, leukocyte differential blood count, thrombocytes, sodium, potassium, creatinine, urea, alkaline phosphatase, ALT, AST, bilirubin, GGT, CK, CRP, PT, APTT, fibrinogen. Frequency tables for qualitative data (gender, age) will be provided. In case a value of one of these parameters is an outlier in a subject, this will be described separately.

In order to check for a potential disbalance of baseline characteristics of the three treatment groups, the Kruskal-Wallis test will be performed for continuous baseline characteristics.

Categorical variables will be compared using the Chi² test for contingency tables.

8.5 Analysis of primary endpoints

The analyses of the endpoints for safety and tolerability will be performed on the full analysis set.

Reported number of Adverse Events and local tolerability

Adverse events (including assessment of local tolerability at the infusion site, which is reported in an AE format as well) will be recorded from the moment of study drug infusion, throughout the study and the follow-up visits. The same accounts for serious adverse events. (S)AEs will be categorized into different organ-systems based on reported symptoms. (S)AEs represent a categorical variable, meaning they are summarized as counts and percentages for different dosage groups. Consequently, no formal data distribution assessment can be performed for this datatype.

An overview of all adverse events (original term) will be generated as subject data listings, including onset relative to start of treatment, duration, intensity, seriousness and potential relationship to the study drug, action taken and outcome. The incidence of treatment-emergent adverse events as well as number of subjects with treatment-emergent adverse events will be summarized by potential relationship to the study drug (certain, probable/likely, possible, unlikely, unrelated) for all treatment groups.

Vital signs

All determined vital signs (oxygenation, heart rate, systolic, diastolic -and mean arterial blood pressure) are registered continuously during the experimental protocol at a measurement frequency once per 5 seconds. Artefacts may be removed. This high-frequency data will first be averaged into 10-minute intervals (calculating simple moving averages), as a correction measure for registration of spurious measurements. The exception for this approach is temperature, for which no high-frequency measurements are performed, meaning no data transformation is required prior to statistical analysis. As vital signs measured during each of the follow-up visits also represent single

Filing: https://fourteenfour.dhcvisioncloud.com/dhcvision/document.jsp?key=DATABASE:1001;IO:1527897

Page 13 of 22

Form Valid From: 08/03/2024

Form Version: 1

Record Title: Clinical Statistical Analysis Plan CT-P1-001

Record Title:

measurements, no data transformation of these measurements is required prior to statistical analysis. Minimum and maximum values for vital signs assessed within one day will be analyzed using descriptive summary statistics (including changes from baseline) by treatment group and time point (Day 1, Day 2, Day 3 etc.).

Data distribution for all vital signs (both averages of high-frequency data and single measurements) will be evaluated using the Kolmogorov-Smirnov test and, if applicable, normal/non-normal distribution will be reported. All variables will be expressed both as mean ± standard deviation (SD), as well as medians and interquartile ranges (IQR) in tables and graphical representations of the data. In case a value of one of these parameters is an outlier in a subject, this will be described separately.

Safety laboratory parameters & inflammatory parameters

All safety laboratory parameters (see the study protocol for a full overview) are measured at set intervals during the experimental protocol, as well as during each of the study's follow-up visits. All safety laboratory measurements represent single timepoint measurements, meaning no data transformation prior to analysis needs to be performed. Complete listings for laboratory values will be generated. Laboratory values outside the normal range will be marked. Minimum and maximum values will be reported (including changes from baseline) by treatment group and time point (Day 1, Day 2, Day 3 etc.). In case a value of one of these parameters is an outlier in a subject, this will be described separately.

Data distribution for all safety laboratory parameters will be evaluated using the Kolmogorov-Smirnov test and normal/non-normal distribution will be reported. All variables will be expressed both as mean ± standard deviation (SD), as well as medians and interquartile ranges (IQR) in tables and graphical representations of the data. In case a value of one of these parameters is an outlier in a subject, this will be described separately.

Results from laboratory tests will be summarized by treatment group and time point using descriptive summary statistics, including changes from baseline. Relative changes (for laboratory values) from baseline to follow-up visits (post-study drug administration minus baseline) will be categorized as:

Maximum increase from baseline: (maximum value post-study drug administration – baseline) / baseline

 \geq 1.5, \geq 2.0

 Maximum decrease from baseline: (baseline - minimum value post-study drug administration) / baseline

≤ 0.5

Form Valid From: 08/03/2024

Form Version:

Record Title: Clinical Statistical Analysis Plan CT-P1-001

Record Title:

A frequency table by treatment dose will be generated for these categorized changes.

In addition, changes from "from within normal range to above normal range" will be evaluated and categorized as:

"changes to at least 1.5-time upper limit normal", "changes to at least twice upper limit normal".

A frequency table by treatment will be generated for these categorized changes from normal at baseline.

In case a value of one of these parameters is an outlier in a subject, this will be described separately.

12-lead ECG parameters

Non-quantifiable differences in ECG's deemed to be of clinical relevance by a clinical investigator will be registered as an (S)AE. For differences in ECG-related (S)AEs, the same ground-rules apply as those listed under reported number of adverse events and local tolerability (please refer to this section). Frequencies of overall interpretation (normal, abnormal and clinically not significant, abnormal and clinically significant) will be tabulated by treatment group and time point.

For numerically quantifiable differences in ECG-parameters (e.g. QTc-time, see the study protocol for a full overview), data distribution will be assessed using the Kolmogorov-Smirnov test and normal/non-normal distribution will be reported. Individual measurement timepoints will be expressed as both mean ± standard deviation (SD), as well as medians and interquartile ranges (IQR).

Extent of exposure

Total exposure [mg] and relative exposure [mg/kg] will be analyzed by descriptive summary statistics.

8.6 **Analysis of secondary endpoints**

Pharmacokinetic data analyses

The PK parameters will be analyzed by descriptive summary statistics. AK1967 concentration-time profiles for individual subjects will be analyzed with non-compartmental approaches using a validated commercially available software package (WinNonlin, version 8.4, Pharsight Corporation, Mountain View, CA). Nominal times will be used in the analysis. For data reported as BLQ and ALQ (below and above limit of quantification, respectively), the low and high limit of detection value will be used in the analysis.

Pharmacokinetic (PK) parameters will be calculated including area under the concentration-time curve (AUC), maximum concentration (C_{max}), time to C_{max} (Tmax), and terminal half-life (t ½).

Form Valid From: 08/03/2024

Form Version:

Record Title: Clinical Statistical Analysis Plan CT-P1-001

The maximum drug concentration (C_{max}) and time to maximum drug concentration (T_{max}) will be determined from observed values. The area under the curve (AUC_{0-t}) will be calculated for PCZ plasma concentration-time profiles using the trapezoidal method derived from non-compartmental analysis from time zero (i.e. start of drug infusion) to the last detectable concentration.

Record Title:

Data distribution will be assessed using the Kolmogorov-Smirnov test and normal/non-normal distribution will be reported. Data will be displayed both tabular and graphically as means ± SD, as well as medians ± IQR. In case a value of one of these parameters is an outlier in a subject, this will be described separately.

Dose proportionality of C_{max} and $AUC_{0-\infty}$ of the different AK1967 dose groups will be calculated by dividing the specific PK parameter by the corresponding value in the lower dose groups and comparing with the corresponding fold change in dose. This is to assess which dosage groups should be reported as being non-dose proportional.

Pharmacokinetic parameters

The following parameters will be determined from the individual plasma concentration-time profiles of AK1967 using non-compartmental methods based on actual relative sampling times:

Single concentration data will be shown with the relevant number of decimal places as provided by the analytical lab. Derived parameters, as far as they do not present single concentrations such as C_{max} , will be listed with an appropriate number of relevant digits (at least 3).

Exposure parameters (C_{max} and AUC_{0-last}) will also be dose-normalized (i.e. divided by dose) for the determination of dose-dependency.

Descriptive pharmacokinetic analyses

The PK analysis will be performed for all active treatment groups.

The individual time courses of the plasma concentrations of AK1967 will be listed and summarized descriptively by treatment group and time point.

Summary statistics by time point will be calculated including only those samples which were taken according to the pre-defined sampling schedule, i.e.: Day 1 (0.5, 1, 1.5, 2, 3, 4, 5, 6, 7, 8, 9, 10, 24 hour ± 2 mins), Day 2 (± 1 hour), Day 3 (± 3 hours), Day 7 (± 1 day), Day 14 (± 2 days), Day 21 ((± 3 days), and Day 28 (± 3 days).

For the calculation of summary statistics, when data is reported as BLQ and ALQ (below and above limit of quantification, respectively), the low and high limit of detection value will be used in the analysis to obtain the means, standard of deviations, coefficient of variation, medians and interquartile ranges.

Form Valid From: 08/03/2024

Form Version:

Record Title:

Record Title: Clinical Statistical Analysis Plan CT-P1-001

Individual plasma concentration-time profiles will be plotted for AK1967 (up to 6 profiles in one plot) for each dose group considering all subjects with available PK concentration data using actual relative sampling times. Mean (SD), as well as median (IQR) of AK1967 plasma concentrations will be plotted for all active treatment groups. Individual and geometric mean concentration versus time curves will be plotted using both linear and semi-logarithmic scaling.

Summary statistics will be calculated for each pharmacokinetic parameter by dose group based on PKs.

Pharmacodynamic data analyses (effects of AK1967 on DPP3 enzyme activity, concentration, reninangiotensin and adrenergic system metabolites)

- To determine the effects of AK1967 on DPP3 activity and concentration in healthy male volunteers.
- To determine the effects of AK1967 on renin-angiotensin system metabolites in healthy male volunteers.
- To determine the effects of AK1967 on circulating adrenergic metabolite concentrations in healthy male volunteers.
- To determine the effects of AK1967 on inflammatory cytokines, including, but not limited to TNF, IL-6, IL-8, IL-10.

Different biomarkers/measurements associated with AK1967's pharmacodynamic activity (see the study protocol for a full overview) are measured at set intervals during the experimental protocol. DPP3 enzyme activity and concentrations measurements are also performed during each of the study's follow-up visits. All pharmacodynamic biomarker measurements represent single timepoint measurements, meaning no data transformation prior to analysis needs to be performed. DPP3 enzyme activity, concentration, adrenergic and renin-angiotensin system metabolite results will be analysed by descriptive summary statistics for the different scheduled determination time points as well as expressed as changes from baseline.

Data distribution for all pharmacodynamic biomarkers will be evaluated using the Kolmogorov-Smirnov test and normal/non-normal distribution will be reported. All variables will be expressed both as mean ± standard deviation (SD), as well as medians and interquartile ranges (IQR) in tables and graphical representations of the data. In case a value of one of these parameters is an outlier in a subject, this will be described separately. Between group differences in pharmacodynamic biomarkers will be assessed using one-way-RM-ANOVA tests (for normally distributed data), or Kruskal-Wallis tests (for non-normally distributed data). In case of a p-value of <0.05 for these tests (implying the presence of dosage groups with differences in a vital sign at a specific timepoint), subsequent Bonferroni or Mann-Whitney-U post-hoc tests will be performed (depending on data distribution), to assess which subgroups are different, and in what direction.

Form Valid From: 08/03/2024

Form Version: 1

Record Title: Clinical Statistical Analysis Plan CT-P1-001

Record Title:

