5.1 Endpoints for the primary objectives

Safety analysis:

The endpoints for the primary objective are to determine over the 28 days study period:

- Reported number of adverse events from baseline (just prior to the start of IMP administration) up until the last follow-up visit 28 days after IMP administration.
- (Changes in) vital signs from baseline to during the first 24 hours after start of IMP administration, as well as during the six follow-up visits. Vital signs included are: heart rate, blood pressure, peripheral oxygen saturation and body temperature.
- Local tolerability at site of i.v. infusion of the IMP.
- Safety laboratory parameters from baseline (just prior to the start of IMP administration) up until the last follow-up visit 28 days after IMP administration. Laboratory parameters included are: Hb, Htc, leukocytes, leukocyte differential blood count, thrombocytes, sodium, potassium, creatinine, urea, alkaline phosphatase, ALT, AST, bilirubin, GGT, CK, CRP, PT, APTT, fibrinogen.
- 12-lead electrocardiogram (ECG) at baseline (screening), compared to ECG's performed 2 hours, 9 hours and 7 days after start of IMP administration.

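### SAP 8.5 applies the same relative-rise and ULN-multiple categories to every laboratory analyte, so the frequency tables by dose are uninformative for tightly regulated and low-baseline analytes

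*SAP*

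**What the plan says.** Laboratory safety is part of the primary endpoint, and SAP 5.1 gives the panel: "Laboratory parameters included are: Hb, Htc, leukocytes, leukocyte differential blood count, thrombocytes, sodium, potassium, creatinine", continuing through liver enzymes, CK, CRP and clotting. Protocol section 10.3.2 adds LDH and albumin.

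SAP 8.5 then sets rule-based categories: "Relative changes (for laboratory values) from baseline to follow-up visits (post-study drug administration minus baseline) will be categorized as".

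- Rise: "Maximum increase from baseline: (maximum value post-study drug administration – baseline) / baseline", with cut-offs of at least 1.5 and at least 2.0.
- Fall: "Maximum decrease from baseline: (baseline - minimum value post-study drug administration) / baseline", with the cut-off printed as ≤ 0.5.
- Shift from normal at baseline to above normal: "changes to at least 1.5-time upper limit normal", and a second category at twice that limit.

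For the rise and fall categories, "A frequency table by treatment dose will be generated for these categorized changes". A second frequency table by treatment covers the shifts. SAP 8.5 names no analyte-specific limit, no shift below the lower limit of normal, and no rule for a zero or near-zero baseline.

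**The concern.** A multiple of baseline or of ULN is a sensible yardstick for an analyte that can range over several-fold. It is a poor one for an analyte held within a narrow band, where a large departure from normal is still a small relative change. It is also poor for an analyte whose baseline is close to zero, where a small absolute change gives a large ratio.

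These are the rule-based counts of laboratory change by dose for a primary endpoint in a first-in-human study with six subjects per arm. A row of zeros for sodium would look like reassurance although the category could not realistically be reached. A scatter of CRP counts could look like a signal although it needs no drug effect. Electrolytes are of particular interest because the drug acts on angiotensin II degradation (protocol sections 2.2 and 3.1) and the protocol also measures renin and aldosterone (Table 8).

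**Working it through.** The plan gives no figure to reproduce here, so the check applies its formulas to example values. The documents give no reference ranges. Those below are assumptions.

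**Step 1: what the cut-offs mean.** The rise formula is a proportional change, so (max − baseline)/baseline ≥ 1.5 means max ≥ 2.5 × baseline, and ≥ 2.0 means max ≥ 3 × baseline. If a fold of baseline was intended, 1.5 means max ≥ 1.5 × baseline. The text does not say so.

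**Step 2: values needed to reach the lowest category.**

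| Analyte | Assumed range | Rise as written (2.5 × baseline) | Rise read as 1.5-fold | 1.5 × ULN | Value at a 50% fall |
|---|---|---|---|---|---|
| Sodium, mmol/L | 135–145 | 337.5–362.5 | 202.5–217.5 | 217.5 | 67.5–72.5 |
| Potassium, mmol/L | 3.5–5.0 | 8.75–12.5 | 5.25–7.5 | 7.5 | 1.75–2.5 |
| Hb, mmol/L | 8.5–11.0 | 21.25–27.5 | 12.75–16.5 | 16.5 | 4.25–5.5 |
| Ht, fraction | 0.40–0.52 | 1.00–1.30 | 0.60–0.78 | 0.78 | 0.20–0.26 |

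Sodium cannot plausibly reach any rise or ULN category on either reading. As written, Ht must equal or exceed its ceiling of 1.

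**Step 3: potassium.** A value of 6.0 to 7.0 is 1.2 to 1.4 times the assumed ULN. The largest relative rise in that span is (7.0 − 3.5)/3.5 = 1.0, below 1.5, and 7.0 is below 1.5 × 5.0 = 7.5 (8.25 if ULN is 5.5). Such a value therefore enters no rise or ULN category as written. On the fold reading, 4.0 to 6.0 is counted (6.0/4.0 = 1.50), but 4.5 to 6.5 (1.44) and 5.0 to 7.0 (1.40) are not.

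**Step 4: the fall category.** As printed (≤ 0.5), sodium 140 to 140 gives 0.00 and is counted, and so is Hb 9.5 to 8.5 (0.105). Hb 9.5 to 4.5 (0.526) is not. If the sign is reversed to a fall of at least 50%, the following are all missed:

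- sodium 140 to 122: 18/140 = 0.13
- potassium 4.0 to 2.6: 1.4/4.0 = 0.35
- Hb 9.5 to 6.0: 3.5/9.5 = 0.37

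**Step 5: low baselines.** CRP 0.5 to 1.3 mg/L gives 0.8/0.5 = 1.6 and is counted as a rise. A baseline of 0, possible for a differential count, gives no defined ratio.

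**Step 6: how often chance alone fills the cells.** A log-normal simulation of 200,000 subjects with no drug effect used assumed within-subject CVs. It took either 6 post-dose samples (the follow-up visits) or 13 (all post-dose biochemistry samples in protocol Table 8).

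| Analyte (assumed CV) | Rise ≥ 1.5 | Fall ≤ 0.5 as printed |
|---|---|---|
| Sodium (1%), Hb (4%), potassium (6%) | 0% | 100% |
| Bilirubin (25%) | 2% to 4% | 84% to 90% |
| CRP (40% to 80%), 6 samples | 17% to 49% | 41% to 67% |
| CRP (40% to 80%), 13 samples | 26% to 62% | 28% to 55% |

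**The case against.** The strongest reply is that nothing is lost. SAP 8.5 requires complete listings with out-of-range results flagged, minima and maxima with change from baseline by group and time point, and a separate description of outliers. With six subjects per arm, one sodium of 122 or potassium of 6.2 would very probably be the group minimum or maximum and be seen. The adverse-event summary in SAP section 9 also takes in laboratory changes, and the DSMB reviews laboratory data after each dose group (protocol section 12.10) without relying on these tables. All of this stands. It limits the point to the quality of the frequency tables.

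A reader might go further and infer that sodium, Hb and Ht can never enter the tables. The documents do not support that. As printed, the fall category takes in practically every result for these analytes. With the sign reversed, a 50% fall in Hb (to 4.25–5.5 mmol/L) or Ht (to 0.20–0.26) is extreme but possible, and on the fold reading Ht of 0.60 from 0.40 would count as a rise.

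A reader might also infer that these are the only categorical laboratory summaries. The adverse-event table contradicts that, although a laboratory change reaches it only if someone records an event, and neither SAP 8.5 nor protocol section 12.2 gives a laboratory criterion for doing so.

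The safeguards still leave a gap. SAP 8.5 plans no count by dose of subjects below the lower limit of normal, and it does not define an outlier.

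**Conclusion.** The point holds as a limited defect in a planned output. The uniform rise and ULN categories cannot discriminate for sodium, practically cannot for Hb and Ht at 2.5 times baseline or 1.5 times ULN, do not capture potassium of 6.0 to 7.0 mmol/L as written, and over-count CRP. Neither reading of the fall category repairs this.

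Individual values remain visible, so it would be wrong to say that abnormal results are missed by the study. The risk is that zero or noisy counts by dose are misread as evidence about the drug.

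The reference ranges and CVs are assumptions. The conclusions on sodium, on rises in Hb and Ht as written, and on near-zero baselines do not depend on their exact values. The potassium and CRP figures do. The change is worth making because it is cheap and adds a low-side summary that the plan lacks.

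**What to change.** In SAP 8.5:

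1. Limit the relative-change and ULN-multiple categories to analytes where multiples are meaningful: ALT, AST, alkaline phosphatase, GGT, bilirubin, CK, LDH and creatinine. In the same edit, state whether 1.5 and 2.0 are proportional changes or folds of baseline, and correct the direction of the fall cut-off.
2. For all analytes, tabulate by dose the subjects who move from within the normal range to below the lower or above the upper local reference limit. The SAP already needs these limits to flag its listings. For sodium, potassium, Hb, Ht, albumin, leukocytes and differential, thrombocytes and clotting, this replaces the relative-change and ULN categories.
3. For CRP and any analyte with a zero or near-zero baseline, report absolute change and count a rise only if the value exceeds ULN.

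The cost is revised SAP wording, one extra table, and fixing the reference limits before unblinding. No new data are needed.

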6.3 General calculation rules

Data will be listed with the observed number of decimal places. Summary statistics will be presented to the same number of decimal places as the observed data, apart from the means and medians (to one more decimal place), and standard deviations (two more decimal places). Calculated data and summary statistics of calculated data will be presented with an appropriate number of decimal places.

In case of replicate measurements (e. g. three determinations of a parameter at one planned timepoint), means of these measurements will be calculated and will be used for summary statistics without any prior rounding.

Form Valid From: 08/03/2024

Form Version: 1

101111 7 6131011

Record Title: Clinical Statistical Analysis Plan CT-P1-001

Record Title:

Data from unscheduled assessments will only be listed and not presented in summary statistics.

Relative study times and dates will be calculated with respect to the start time and date of the administration of study drug.

Calculation of relative days from onset of adverse events:

The relative day for onset of an adverse event is calculated as "day of onset" minus "day of start of treatment".

Duration of adverse events:

The duration of an adverse event (expressed in days) is calculated as "stop date" minus "start date" plus 1.

If parts of the start/stop date of an adverse event are missing (day, month, or year), the relative day for onset and/or the duration of the adverse event are not calculated.

In order to determine if an adverse event or the worsening of an adverse event is a treatmentemergent event, the following rules will be used as a worst-case scenario:

- If the date (and time) of onset or change is completely known, the adverse event is considered as treatment-emergent, provided the day (and time) of onset or change is after or on the same day (and time) as first study treatment.
- If the time of onset or change is missing, but the day, month and year is known, the adverse event is considered as treatment-emergent, provided the day of onset or change is after or on the same day as first study treatment, unless other information (e.g. stop date/time) suggest otherwise.

Calculation of absolute changes from baseline:

- post-dose value - baseline value

Calculation of relative changes from baseline:

- (post-dose value - baseline value)/baseline value

Frequencies / percentages for qualitative data:

- Number of observations (frequency)
- Percent

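### As printed, the laboratory maximum-increase categories start at 2.5 and 3 times baseline, so a 1.5-fold rise or a doubling is not counted in that frequency table; the cut-offs look like fold limits placed on a relative-change formula

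*SAP*

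**What the plan says.** Safety laboratory values are part of the primary endpoint (protocol section 4; SAP 5.1). SAP 8.5, under safety laboratory and inflammatory parameters, introduces a set of categories: "Relative changes (for laboratory values) from baseline to follow-up visits (post-study drug administration minus baseline) will be categorized as".

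- **Rises:** "Maximum increase from baseline: (maximum value post-study drug administration – baseline) / baseline", cut-offs ≥ 1.5 and ≥ 2.0.
- **Falls:** "Maximum decrease from baseline: (baseline - minimum value post-study drug administration) / baseline", cut-off ≤ 0.5.
- **Output:** "A frequency table by treatment dose will be generated for these categorized changes".

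The general rule for relative change in SAP 6.3 subtracts baseline in the same way: "post-dose value - baseline value)/baseline value" (opening bracket omitted).

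A second frequency table in SAP 8.5 covers men whose value was within the normal range at baseline. Its categories are "changes to at least 1.5-time upper limit normal" and "changes to at least twice upper limit normal".

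The same section also plans complete listings ("Laboratory values outside the normal range will be marked"), descriptive summaries with changes from baseline, minimum and maximum values by group and time point, and separate description of outliers.

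**The concern.** The cut-offs and the formula do not seem to belong together. Limits of 1.5 and 2.0 are natural for a ratio to baseline, where 1 means no change. The printed formula is that ratio minus 1, where 0 means no change. A programmer following the text would produce a table that starts counting at a 2.5-fold rise. Nothing would flag the mismatch, because SAP 6.3 defines relative change in the same way.

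At stake is how well one by-dose safety table does its job. The primary endpoint is analysed descriptively, with 6 men per dose and 6 on placebo. In groups of that size a count of individual men with marked rises is informative, since a mean or median can dilute one man's rise. This is the only planned categorical count of rises against each man's own baseline.

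**Working it through.** **Inputs.** The formulas and cut-offs are those of SAP 8.5. Let B be baseline, and max and min the largest and smallest post-dose values. The documents give no expected count for this table, so there is no figure to reproduce. The check is algebra.

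**Step 1: rises.** (max − B)/B ≥ c is the same as max/B ≥ 1 + c. So ≥ 1.5 means max ≥ 2.5 B, and ≥ 2.0 means max ≥ 3 B.

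| max/B | Score on printed formula | Printed ≥ 1.5 | Printed ≥ 2.0 | Ratio ≥ 1.5 | Ratio ≥ 2.0 |
|---|---|---|---|---|---|
| 1.0 | 0 | no | no | no | no |
| 1.5 | 0.5 | no | no | yes | no |
| 2.0 | 1.0 | no | no | yes | yes |
| 2.49 | 1.49 | no | no | yes | yes |
| 2.5 | 1.5 | yes | no | yes | yes |
| 3.0 | 2.0 | yes | yes | yes | yes |

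An illustrative creatinine baseline of 80 µmol/L (an assumed value) must reach 80 × 2.5 = 200 and 80 × 3 = 240. Read as ratios, the limits would be 80 × 1.5 = 120 and 80 × 2 = 160.

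**Step 2: falls, as evidence of the intended scale.** (B − min)/B ≤ 0.5 is the same as min/B ≥ 0.5.

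| min/B | Score on printed formula | Printed ≤ 0.5 | Ratio ≤ 0.5 |
|---|---|---|---|
| 1.0 | 0 | counted | not counted |
| 0.7 | 0.3 | counted | not counted |
| 0.5 | 0.5 | counted | counted |
| 0.4 | 0.6 | not counted | counted |
| 0.2 | 0.8 | not counted | counted |

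As printed, the row counts men with no change and leaves out those who lost more than half. It makes sense only as min/B ≤ 0.5. Read that way, 0.5, 1.5 and 2.0 form one coherent set of fold-of-baseline limits. The adjacent ULN categories use 1.5 and 2 as multiples too, though of a different reference.

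**Step 3: what the ULN table picks up.** Let the baseline be b × ULN.

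- *Normal at baseline (b ≤ 1).* A doubling reaches 2b × ULN. It meets 1.5 × ULN only if b ≥ 1.5/2 = 0.75, and 2 × ULN only if b = 1. From b = 0.9 it reaches 1.8 × ULN and is counted in the first category. From b = 0.5 it reaches 1.0 × ULN and is in neither frequency table.
- *Above the ULN at baseline (b > 1).* The ULN table does not apply. Exclusion criterion 6 in protocol 6.3 removes only men with liver tests above 2 × ULN, so such baselines are possible. ALT rising from 1.5 to 3.6 × ULN is a 3.6/1.5 = 2.4-fold rise, which scores 1.4 and enters neither table. From a baseline of 2 × ULN, any rise short of 2 × 2.5 = 5 × ULN enters neither.

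**The case against.** The strongest reply is that the SAP is consistent about its scale. The general rule in 6.3, the lead-in and the formula in 8.5 all subtract baseline, and no sentence calls 1.5 and 2.0 folds. The ULN categories are multiples of something else and do not by themselves fix the meaning of the baseline cut-offs. It stands that intent is inferred. The decrease row is what makes the inference strong, because it cannot be used sensibly on the printed scale.

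The second reply concerns importance, and much of it stands. A reader might infer that a doubling of creatinine, ALT or bilirubin would be reported as no event, or would be visible only in listings, or that this is the only by-dose summary of change from baseline. The documents do not support any of these. SAP 8.5 plans change-from-baseline summaries and minimum and maximum values by group and time point, and SAP 6.3 includes the maximum among its standard statistics. With 6 men per arm, the largest individual change will therefore show. Outliers are described separately. SAP section 9 lists a change-from-baseline laboratory table by dosing group and an adverse event table that takes in laboratory changes. The ULN table also catches part of the gap. For example, creatinine going from 80 to 190 µmol/L is missed here (score 110/80 = 1.375), but it meets 1.5 × ULN for any ULN up to about 126 (190/1.5). The documents give no ULN, so that figure is conditional.

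It is also fair that no decision rule uses these categories. The DSMB reviews an interim safety report per dose group (protocol 10.3 and 12.10), and SAP section 9 does not list this frequency table by name. Finally, near-empty rows for tightly regulated analytes are mostly a result of using one relative cut-off for every analyte, and a ratio scale would not cure that.

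**Conclusion.** The point holds, limited to this frequency table. The arithmetic is exact: the printed increase categories mean 2.5 and 3 times baseline, and a 1.5-fold rise or a doubling is counted in neither. That fold-of-baseline limits were meant is an inference, well supported by the decrease row and, less directly, by the ULN categories. No text says that 2.5-fold and 3-fold were intended.

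The gap left by both frequency tables together is narrower than the formula alone suggests. It covers doublings from below 0.75 × ULN, and rises of less than 2.5-fold from a baseline already above the ULN. Those rises can still be seen in the other summaries, listings and descriptions. The plan should be corrected because this table supports a primary safety endpoint and could look emptier than its cut-offs imply. The trial's data and its escalation decisions do not depend on it.

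**What to change.** In SAP 8.5, define the increase categories as maximum post-dose value divided by baseline, ≥ 1.5 and ≥ 2.0. Equivalently, keep the printed formula and set the cut-offs to ≥ 0.5 and ≥ 1.0. In the same edit, define the decrease category as minimum post-dose value divided by baseline, ≤ 0.5. Label the table *fold of baseline*. Correcting the decrease row alone would leave the increase row wrong. If 2.5-fold and 3-fold were intended, the SAP should say so explicitly.

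The cost is a short SAP edit and the matching program lines, with no new data. More men will be counted, some of them because of noise in variable markers such as CRP and CK. The placebo column shows that background.
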